6.4 Duration of Follow Up

Patients will be followed for a minimum of 30 days after the last radiation therapy fraction is administered for adverse events monitoring, unless otherwise specified in this section of the protocol. A different time frame may be longer but not shorter than 30 days unless a specific scientific rationale is presented to suggest that a shorter window can be used to identify events. Follow-up for serious adverse events and mortality after the last study dose is administered will take place during the routine clinic visits that the patient will have during the 30 day follow-up window (Also referenced in Appendix D). If no visit occurs during this window, a phone call confirmation should be made to the patient to determine vital status and whether any adverse events and in particular, Grade 4 unexpected adverse events occurred during that window of time and recorded on Appendix F.

Patients will be followed 25 months or until death after the last study radiation treatment for monitoring survival study endpoints.

6.5 Criteria for Removal from Study

Patients may be removed from study when any of the criteria listed in section 6.3 applies.

7.0 Dosing Delays/Dose Modifications

7.1 Any Grade 3 or higher acute toxicity with the exception of hematologic and laboratory toxicity may result in a treatment break at the discretion of the treating investigator until it resolves to Grade 2 or less. Duration of treatment break is at the discretion of the treating radiation oncologist. All labs will

be assessed by the treating physician to determine whether they are considered clinically significant or not clinically significant and treatment will be held at their discretion.

8.0 Measurement of Effect

8.1 Antitumor Effect – Solid Tumors

Response and progression will be evaluated in this study using the Response Evaluation Criteria in Solid Tumors (RECIST) criteria 1.1. Changes in the largest diameter (unidimensional measurement) of the tumor lesions and the shortest diameter in the case of malignant lymph nodes are used in the RECIST criteria.

8.1.1 Survival Outcomes

Progression-Free Survival is defined as the duration of time from the start of treatment to the time of progression, death, or date of last contact; those lost to follow-up will be censored.

Overall Survival is defined as the duration of time from the start of treatment to date of death or date of last contact; those lost to follow-up will be censored.

9.0 Adverse Events List and Reporting Requirements

9.1 Adverse Event List for Hypofractionated Thoracic Radiotherapy

9.1.1 Cardiac and Pericardial Injury

9.1.1.1

Although acute cardiac and pericardial injury is uncommon in the conventionally fractionated course of RT, with larger doses per fraction of this study, a number of possible side-effects can be seen.

9.1.1.2

Dose to the heart has been shown to impact long term overall survival. All attempts to minimize dose to the heart will be made in accordance with the dose constraints in Section 6.2.1

9.1.2 Gastrointestinal/Esophageal Injury

9.1.2.1

The radiation effects on the esophagus can be acute: esophagitis (i.e., dysphagia, causing pain on swallowing, typically relatively soon after RT course is completed, and typically resolves on its own within days to a week or longer), or chronic, typically manifesting with dysphagia due to stenosis, or esophageal ulceration, with perforation in the extreme cases. The stomach and small bowel are also susceptible to radiation injury that manifests as nausea, anorexia, and vomiting (acute) or stenosis, ulceration, or rarely perforation (late). The liver is exquisitely sensitive to radiation therapy. Acute manifestation of liver toxicity is usually reflected by increasing hepatic enzymes (AST and ALT), as well as nausea. Late radiation hepatotoxicity is extraordinarily rare when treating intrathoracic malignancies, as large amounts of the liver can be irradiated to high doses as long as an adequate volume of liver is spared and the mean dose is kept below 30 Gy (see Section 6.2.1).

9.1.3 Central Airway/Bronchial Injury

9131

Severe injury to the proximal tracheobronchial tree, resulting in fistula formation or hemoptysis, which may be fatal, is possible but rare (<5%). This bronchial injury with subsequent focal collapse of lung may impair overall pulmonary status. It also makes further assessment of tumor response more difficult as the collapsed lung approximates the treated tumor. Because atelectatic lung and tumor have similar imaging characteristics, radiology reports will often describe the overall process as progressive disease while the actual tumor may be stable or shrinking. The consequences of bronchial toxicity, e.g., cough, dyspnea, hypoxia, impairment of pulmonary function test parameters, pleural effusion or pleuritic pain (associated with collapse), should all be graded according to the Common Terminology Criteria for Adverse Events (CTCAE), v. 5.0;

9.1.4 Lung Injury

9.1.4.1

Radiation pneumonitis is a subacute (weeks to months from treatment) inflammation of the end bronchioles and alveoli. Radiation fibrosis is a late manifestation of radiation injury to the irradiated lung. It is very important that a Radiation Oncologist participate in the care of the patient, as the clinical picture may be very similar to acute bacterial pneumonia, with fatigue, fever, shortness of breath, nonproductive cough, and a pulmonary infiltrate on chest x-ray. The infiltrate on chest x-ray should include the area treated to high dose, but may extend outside of these regions. The infiltrates may be characteristically "geometric" corresponding to the radiation portal, but may also be ill defined. Patients reporting symptoms as above will be promptly evaluated and treated. Mild radiation pneumonitis may be treated with nonsteroidal anti-inflammatory agents or steroid inhalers. More significant pneumonitis will be treated with systemic steroids, bronchodilators, and pulmonary toilet. Supra- and concurrent infections should be treated with antibiotics. Consideration of prophylaxis of opportunistic infections should be considered in immunocompromised patients.

9.1.5 Spinal Cord or Brachial Plexus Injury

9.1.5.1

Radiation myelitis and brachial plexopathy are rare late effects of radiation therapy (<1%). In the extremely rare cases where radiation myelitis occurs, common symptoms include neuropathic pain, progressive weakness, and sensory changes. Radiation-induced brachial plexopathy presents in a similar fashion to radiation myelitis, with symptoms being limited to areas innervated by the affected brachial plexus.

9.1.6 Chest wall pain/rib fractures

9.1.6.1

Chest wall pain and/or pathologic rib fractures are uncommon complications of radical radiotherapy that are most frequently seen in the setting of SBRT to very peripheral lung lesions. The most common symptom of the syndrome is pain in an area of the chest wall in very close proximity to high dose areas which typically responds to NSAIDs.

9.2 Adverse Event Characteristics

 CTCAE term (AE description) and grade: The descriptions and grading scales found in the revised NCI Common Terminology Criteria for Adverse Events (CTCAE) version 5.0 will be utilized for AE reporting. All appropriate treatment areas should have access to a copy of

the CTCAE version 5.0. A copy of the CTCAE version 4.0 can be downloaded from the CTEP web site (http://ctep.cancer.gov).

- **'Expectedness'**: AEs can be 'Unexpected' or 'Expected' (see Section 7.1 above) for expedited reporting purposes only.
- **Attribution** of the AE:
- Definite The AE is clearly related to the study treatment.
- Probable The AE is likely related to the study treatment.
- Possible The AE may be related to the study treatment.
- Unlikely The AE is doubtfully related to the study treatment.
- Unrelated The AE is clearly **NOT related** to the study treatment.

9.3 STRC SAE Reporting Requirements

The Data Safety Monitoring Committee (DSMC) is responsible for reviewing SAEs for WFBCCC Institutional studies as outlined in Appendix D. All Adverse Events that occur during protocol intervention and are coded as either 1) unexpected grade 4, 2) unplanned inpatient hospitalization ≥ 24 hours (regardless of grade), or grade 5 (death) must be reported to the DSMC using the using the SAE console in WISER.

All WFBCCC Clinical Protocol and Data Management (CPDM) staff members assisting a Principal Investigator in investigating, documenting and reporting an SAE qualifying for DSMC reporting are responsible for informing a clinical member of the DSMC as well as the entire committee via the email notification procedure of the occurrence of an SAE.

9.4 WFUHS IRB AE Reporting Requirements

Any unanticipated problems involving risks to subjects or others and adverse events shall be promptly reported to the IRB, according to institutional policy. Reporting to the IRB is required regardless of the funding source, study sponsor, or whether the event involves an investigational or marketed drug, biologic or device. Reportable events are not limited to physical injury, but include psychological, economic and social harm. Reportable events may arise as a result of drugs, biological agents, devices, procedures or other interventions, or as a result of questionnaires, surveys, observations or other interactions with research subjects.

All members of the research team are responsible for the appropriate reporting to the IRB and other applicable parties of unanticipated problems involving risk to subjects or others. The Principal Investigator, however, is ultimately responsible for ensuring the prompt reporting of unanticipated problems involving risk to subjects or others to the IRB. The Principal Investigator is also responsible for ensuring that all reported unanticipated risks to subjects and others which they receive are reviewed to determine whether the report represents a change in the risks and/or benefits to study participants, and whether any changes in the informed consent, protocol or other study-related documents are required.

Any unanticipated problems involving risks to subjects or others occurring at a site where the study has been approved by the WFUHS IRB (internal events) must be reported to the WFUHS IRB within 7 calendar days of the investigator or other members of the study team becoming aware of the event.

Any unanticipated problems involving risks to subjects or others occurring at another site conducting the same study that has been approved by the WFUHS IRB (external events) must be reported to the WFUHS IRB within 7 calendar days of the investigator or other members of the study team becoming aware of the event.

Any event, incident, experience, or outcome that alters the risk versus potential benefit of the research and as a result warrants a substantive change in the research protocol or informed consent process/document in order to insure the safety, rights or welfare of research subjects.

10.0 Data Management

Informed consent document	EPIC
Protocol registration form	WISER/OnCore
Pre-Toxicity	WISER/OnCore
Off study, Off treatment, Withdrawal	WISER/OnCore
Vitals Form	REDCap
Con-med PRN Form	WISER/OnCore
Follow up Post Washout	REDCap
Treatment Response Evaluation	REDCap
Pattern of Progression	REDCap
Adverse Events Log	WISER/OnCore
Mandatory Target Coverage/Dose Constraint	REDCap
Compliance Confirmation	

This project will utilize REDCap Clinical Data Interoperability Services. This is a special feature for importing data into REDCap from WakeOne. It provides an adjudication process whereby REDCap users can approve all incoming data from WakeOne before it is officially saved in their REDCap project. REDCap Clinical Data Interoperability Services can only be enabled by a REDCap administrator who serves as an honest broker to PHI. REDCap's Clinical Data Interoperability Services can only be accessed by users with valid WakeOne credentials. Using the Clinical Data Interoperability Service requires using the Medical Record Number (MRN) as a key to automatically gather demographics and laboratory data and reduces data entry errors.

11.0 Statistical Considerations

With the exception of our primary aim, which is comparative and hypothesis-testing (relative to a historical control), the rest of our analysis plan is largely descriptive in nature.

11.1 Analysis of Primary Objective

11.1.1 We will compare the proportion of the sample with any in-field progression at 2 years to the historical control proportion of 0.5, using a one-sample z-test. We expect that a proportion

(around 10-15%) of our initial baseline sample will be missing data on this primary outcome at 2 years, and therefore we have correspondingly increased our target recruitment by this percentage (see section 11.3 below).

11.2 Analysis of Secondary Objective

- 11.2.1 We will compute the proportion of the sample developing any toxicity of grade 2 or higher over the 25 months, and construct a corresponding 95% confidence interval.
- 11.2.2 We will compute proportions of patients who have experienced local progression by 13 months (1 year following first post-radiotherapy scan) and by 25 months (2 years following first post-radiotherapy scan), and will also compute the same two proportions considering regional progression, distant progression, and any (of the 3 categories) progression. We will construct 95% confidence intervals around these proportions. Those patients for whom we are unable to determine progression status at 1 and 2 years (e.g., because they do not return for the necessary scans, or because they die without evidence of progression) will be left out of these analyses. We will evaluate PFS and OS first using the Kaplan-Meier lifetable method, and will estimate median survival and corresponding 95% CIs; we will also explore simple Cox proportional hazards models of each of these survival outcomes, to examine the predictive influence of variables such as age, gender, ECOG performance status, stage at diagnosis, PTV 7000+6750 volume, and PTV 5750 volume. Patients who are lost to follow-up will be censored at that time in these analyses.

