2.2 Secondary Objective(s)

- 2.2.1 To determine the toxicity profile of thoracic HRT consisting of 70 Gy in 25 fractions as graded by CTCAE version 5.0
- 2.2.2 To determine proportion with local, regional, and distant progression at 1 and 2 years after the first post-radiotherapy scan, and compute progression-free and overall survival (PFS and OS, respectively).

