5.2 Secondary Outcomes

- 5.2.1 Toxicities will be evaluated per CTCAE Version 5.0 one month following completion of therapy and then every 3 months thereafter until 25 months from completion of radiation therapy.
- 5.2.2 Patterns of progression will be defined as follows: Local progression will be defined as in field progression (see Section 5.1.1); regional progression will be defined as any new regional lymphadenopathy in the hilum or mediastinum that was not included in the gross tumor volume (GTV); distant progression will be defined as any radiographic or pathologic evidence of disease outside the primary tumor and regional lymph nodes, including subsequent pulmonary parenchymal lesions. Progression-free survival will be evaluated by considering the time from registration to progression of disease or death; those who do not experience either outcome will be censored at date of last visit. Overall survival will be evaluated by considering the time from registration to death from any cause; those who do not die will be censored at date of last visit. Progression will be assessed through CT scans administered immediately following treatment and then every 3 months after that, out to 25 months.

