6.3 Duration of Therapy/Study Follow-up

Treatment may continue until the completion of radiotherapy or until one of the following criteria applies:

- Disease progression
- Intercurrent illness that prevents further administration of treatment or ability to present for follow-up visits (i.e. hospitalized)
- Unacceptable adverse event(s)
- Patient decides to withdraw from the study, or further follow-up on study
- General or specific changes in the patient's condition that render the patient unacceptable for further treatment in the judgment of the investigator
- If patients have disease progression or require further radiation treatment outside the protocol, they will be treated at the discretion of their treating physician. They will be followed for local control and survival for 25 months after they have completed their initial radiation.

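### The only toxicity estimate is a crude 25-month proportion with no stated denominator and no allowance for incomplete toxicity follow-up

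*Combined protocol and SAP*

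**What the plan says.** Secondary objective 2.2.1 is "To determine the toxicity profile of thoracic HRT consisting of 70 Gy in 25 fractions as graded by CTCAE version 5.0". The analysis in section 11.2.1 is one sentence: "We will compute the proportion of the sample developing any toxicity of grade 2 or higher over the 25 months", with a 95% confidence interval. No other toxicity rate is planned. The stopping criterion in section 11.6 is a count of five patients with specified grade 4 or 5 events, not an estimate.

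On follow-up, section 5.2.1 sets the schedule: "Toxicities will be evaluated per CTCAE Version 5.0 one month following completion of therapy and then every 3 months thereafter until 25 months". Other sections make it foreseeable that some patients will not complete it:
- Section 6.4 sets a floor: "Patients will be followed for a minimum of 30 days after the last radiation therapy fraction is administered for adverse events monitoring".
- Sections 6.3 and 6.5 allow removal for progression, intercurrent illness, adverse events or withdrawal.
- For patients who progress or need radiation outside the protocol, section 6.3 says only: "They will be followed for local control and survival for 25 months after they have completed their initial radiation". Toxicity is not named.

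Section 11.2.2 does give rules for other endpoints. Patients of undetermined progression status are left out of the progression proportions. For PFS and OS, "Patients who are lost to follow-up will be censored at that time in these analyses". No such rule is attached to toxicity.

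**The concern.** A proportion described as covering 25 months is well defined only if every patient is observed for 25 months, or has the event or dies first. Take a patient last assessed for toxicity at month 4 without an event. Section 11.2.1 does not say whether that patient is a non-event, is excluded, or contributes four months of observation. The first two choices give different answers, and neither uses the partial follow-up properly.

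The harms that follow-up exists to capture are the ones most exposed. Section 9.1.2 describes chronic esophageal stenosis and ulceration. Section 9.1.4 places pneumonitis at weeks to months and adds: "Radiation fibrosis is a late manifestation of radiation injury to the irradiated lung". Patients who leave early cannot contribute such events. At stake is the toxicity rate reported for a dose-escalated regimen. Its confidence interval would not reflect the unobserved time, and the choice of denominator could be made after the data are seen.

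Deaths are not the difficulty. A patient who dies without toxicity is properly a non-event in a cumulative incidence. The difficulty is patients who are alive but no longer assessed.

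**Working it through.** **Figures in the plan.** The documents give no expected toxicity rate, survival rate or loss from toxicity assessment. The nearest figure is in sections 11.1.1 and 11.3.1: 10-15% of patients without primary-outcome data at 2 years. The sample size built on it reproduces: (1.645 + 0.842)² × 0.25 / 0.25² = 24.7, so 25 evaluable; 25 / (1 − 0.15) = 29.4, so 30 recruited. This bears on the wording. Section 11.1.1 also speaks of a proportion of *the sample*, and there the analysed number is 25 of 30. The phrase alone therefore does not settle the toxicity denominator.

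**Step 1: direction of bias.** Let p be the true 25-month incidence, d the share whose toxicity follow-up ends early (independently of toxicity), and f the share of those patients' toxicities that occur before follow-up ends.
- All patients in the denominator: p × [1 − d(1 − f)].
- Event-free early leavers dropped, early events kept: p × [1 − d(1 − f)] / [(1 − d) + d·p·f].

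Assumed p = 50%:

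| d | f | All patients | Event-free leavers dropped |
|---|---|---|---|
| 10% | 0 | 45.0% | 50.0% |
| 10% | 0.8 | 49.0% | 52.1% |
| 15% | 0 | 42.5% | 50.0% |
| 15% | 0.8 | 48.5% | 53.3% |

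The first reading is 1 to 7.5 points low. The second is 0 to 3.3 points high. Toxicity recorded before loss still counts, so the downward bias shrinks as f rises.

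**Step 2: expected size.** Assume constant monthly hazards for toxicity (t), death (m) and loss alive (c) over 25 months.
- True incidence: t/(t+m) × [1 − exp(−25(t+m))].
- Whole-sample proportion: t/(t+m+c) × [1 − exp(−25(t+m+c))].

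Worked case, assuming 2-year survival of 50%: m = −ln(0.50)/24 = 0.0289. A true incidence of 30% needs t = 0.0210. A 10% incidence of loss, with death competing, needs c = 0.0060. The whole-sample proportion is then 0.0210/0.0559 × [1 − exp(−1.397)] = 28.3%. With 15% loss it is 27.4%. A true 60% reads 57.2% and 55.7%.

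Results for assumed 2-year survival of 35%, 50% and 65%:
- True 30%, 10-15% loss, all patients in the denominator: 27.2% to 28.4%. If 10-15% is instead taken as the probability of loss in the absence of death, 28.0% to 28.9%.
- True 30%, event-free leavers dropped: 30.4% to 31.4% over both definitions of loss.
- Relative understatement for true rates of 15%, 30% and 60%, all patients in the denominator: 4.6% to 9.9% on the first definition of loss, about 3% to 7% on the second.
- With only 3-5% lost alive: about 1% to 3% relative.

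**Step 3: extreme bound.** If every patient with incomplete follow-up had an unrecorded toxicity, the error would be 3/30 = 10 points to 5/30 = 16.7 points. Five of 30 is 15% (4.5 patients) rounded up.

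**Step 4: sampling error.** The exact 95% interval is 15% to 49% for 9/30 and 31% to 69% for 15/30.

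**The case against.** A reader might infer that section 11.2.1 counts patients who leave early as toxicity-free, so that the rate can only err downward. The documents do not say this. The denominator is undefined, the same phrase covers an evaluable subset in the primary analysis, and on that reading the bias is zero or upward. A reader might also infer that toxicity alone lacks an allowance for time observed. That is not so: the progression proportions in section 11.2.2 exclude undetermined patients but use no time at risk either. Only PFS and OS do.

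The size is also open to challenge, and these points stand. The 10-15% is stated for the primary outcome, not for toxicity assessment. Section 11.2.2 lists death without progression as a reason for undetermined status, so the 10-15% may include deaths, which are not a source of bias here. Constant hazards sit poorly with acute esophagitis soon after treatment and pneumonitis at weeks to months, and adverse events are assessed weekly during treatment and at one month (section 6.1). Much grade 2 or higher toxicity may be recorded before anyone is lost. The expected bias is well inside the sampling error. Section 11.0 calls the secondary analyses largely descriptive, and the stopping count does not depend on this estimate.

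None of this supplies the missing denominator or a rule for incomplete follow-up. The loss could also exceed 10-15%, because toxicity assessment is not named after progression.

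**Conclusion.** The point holds as a defect of definition and method, with modest expected size. Section 11.2.1 specifies one crude proportion, and both natural ways of computing it can be biased when toxicity follow-up is incomplete, in opposite directions. On assumed constant hazards, 2-year survival of 35-65% and 10-15% lost alive, a true 30% reads about 27-29% with all patients in the denominator and 30-31% with event-free leavers dropped. These rest on assumptions, not on figures in the documents. The bias is smaller with fewer losses or early toxicity, and larger for late events. The 10-17 point figure is an extreme bound and should not be read as an expectation. A claim that the toxicity rate is necessarily understated is not supported. The change is worth making because toxicity is a stated secondary objective, the error is systematic and outside the confidence interval's scope, and the remedy is cheap.

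**What to change.** In section 11.2.1, define the analysis set as patients who received at least one fraction. Report the 25-month cumulative incidence of first grade 2 or higher toxicity by the Aalen-Johansen estimator, with death without toxicity as a competing event and all other patients censored at their last adverse-event assessment. Give its 95% confidence interval. Report beside it the observed count and the number with incomplete toxicity follow-up. Use the same estimator for any late or higher-grade rate. Do not censor deaths in a Kaplan-Meier analysis of toxicity, as that would overstate the incidence.

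The cost is a change of SAP wording and a few lines of code, with no new patients. Onset dates are on the adverse event log (Appendix F), death dates come from the data collected for OS, and censoring dates from the follow-up visits. The off-study form (Appendix H) is not enough alone: it has no death-date field, and its date of last contact need not be the date of the last adverse-event assessment.

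There are two downsides. The interval will be slightly wider. The estimator also assumes censoring independent of toxicity, which may fail for patients whose toxicity assessment stops at progression. The plan should state that as a limitation.

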2.0 Objectives

2.1 Primary Objective(s)

2.1.1 To determine the in-field control of hypofractionated radiotherapy consisting of 70 Gy in 25 fractions without concurrent chemotherapy measured at two years after the first post-radiotherapy scan.

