5.0 Study Outcomes and Study Measures

5.1 Primary Outcome

5.1.1 The primary outcome measure will be presence/absence of any in-field progression by 2 years. In-field progression is defined as growth of the targeted lesions beyond the treated volume. The treated volume will be defined as the 28.75 Gy isodose line (50% of 57.5 Gy). Pathologic confirmation of tumor progression is preferred, but can be determined radiographically by Multidisciplinary Thoracic Oncology Program consensus if biopsy of the lesion in question is not feasible or safe.

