11.3 Power and Sample Size

11.3.1 Prior studies suggest an average proportion of 0.50 of patients who are free from in-field progression at 2 years following standard radiotherapy alone. ^{4,9} Based on prior reports of dose escalated hypofractionated radiotherapy and our institutional experience using a similar dose fractionation scheme, we hypothesize that HRT will improve 2 year freedom from in-field progression from this 50% to 75%. ^{1,2,22} With a sample size of n=25, we will have 80% power to detect this increase, assuming a one-tailed α of 0.05. We anticipate that approximately 10% -15% of patients recruited will not provide data on our primary outcome at 2 years, so we anticipate recruiting n=30 patients total to allow us to have a total n of 25 for our primary analysis.

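### Section 11.2.2 drops deaths without progression but keeps progressors, and the primary test on the same event does not say how such deaths count

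*Combined protocol and SAP*

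**What the plan says.** Section 11.2.2 computes the proportions with local, regional, distant and any progression at 13 and 25 months. Patients whose status cannot be determined, whether through missed scans "or because they die without evidence of progression) will be left out of these analyses". Those who progressed have a known status and remain in numerator and denominator, even if they die later.

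The primary endpoint is the same event. Section 5.1.1 reads "The primary outcome measure will be presence/absence of any in-field progression by 2 years", and 5.2.2 defines local progression by pointing back to 5.1.1. The time is also the same: 2.1.1 has control "measured at two years after the first post-radiotherapy scan", and 11.2.2 equates 25 months with that point.

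For the primary analysis, 11.1.1 specifies a one-sample z-test against 0.5 and expects that around 10-15% "of our initial baseline sample will be missing data on this primary outcome at 2 years". Section 11.3.1 sets n=25 for 80% power (50% versus 75% free, one-sided 5%), "so we anticipate recruiting n=30 patients total to allow us to have a total n of 25 for our primary analysis". Neither section, nor 5.1.1, mentions death. Death is handled explicitly only for PFS, OS and the 11.2.2 proportions.

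**The concern.** A patient who dies before 2 years without in-field progression could count as controlled, as failed or as missing. The plan's only hypothesis test depends on which, and the choice is unwritten.

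The complete-case wording of 11.1.1 and 11.3.1, next to the 11.2.2 rule, points towards treating these patients as missing. That is not a neutral loss. Every patient removed this way was controlled when last seen, while every progressor is kept. The analysed sample therefore looks worse than the treated sample, and recruiting 30 to obtain 25 repairs only the number, not the mix.

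For the secondary proportions the rule is explicit, so the distortion follows from carrying out the plan as written.

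**Working it through.** **Inputs.** From 11.1.1 and 11.3.1: 50% versus 75% free, one-sided 5%, z-test, 25 evaluable, 30 recruited, 10-15% missing. Assumed: all 30 treated, no other losses, *progression* in the 11.2.2 rule read as local progression, and the number of deaths k. The documents give no death rate for this trial, so k is varied.

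**The plan's own figure.** Null-variance z formula: n = [(1.645 + 0.842) × 0.5 / 0.25]² = 24.7, so 25. Recruitment: 25/0.85 = 29.4, so 30. Both reproduce. Exactly, the z-test at n=25 rejects at 17 or more free, with power 0.851 and type I error 0.054. At n=30 it rejects at 20 or more.

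**Effect on the 11.2.2 proportions.** With X progressors and k deaths dropped, the plan reports X/(30−k). Cumulative incidence is X/30, so the ratio is 30/(30−k): 1.20 for k=5, 1.30 for k=7 and 1.50 for k=10. With X at its expected 7.5 (25% of 30), the plan would report 30.0%, 32.6% and 37.5% against 25%.

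**Power if the exclusion is carried to the primary test.** Let c(m) be the z-test cutoff for m analysed patients.

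- *Crude reading of 75%:* X ~ Bin(30, 0.25) and the k deaths all fall among controlled patients. The test rejects if 30 − k − X ≥ c(30−k).
- *Actuarial reading:* independent constant hazards λp and λd, with exp(−2λp) = 0.75 and λd set so that k deaths are expected. Let S = exp(−2λd) and F = λp/(λp+λd) × [1 − exp(−2(λp+λd))]. Apparent control is 0.75S/(F + 0.75S), with binomial power at 30−k.
- *Random loss:* the same k patients lost regardless of outcome, so control stays 75%.

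| Deaths dropped | Analysed | Cutoff | Crude | Actuarial | Random loss |
|---|---|---|---|---|---|
| 1 | 29 | 19 | 0.894 | 0.906 | 0.915 |
| 2 | 28 | 19 | 0.803 | 0.838 | 0.862 |
| 3 | 27 | 18 | 0.803 | 0.855 | 0.887 |
| 4 | 26 | 18 | 0.674 | 0.761 | 0.820 |
| 5 | 25 | 17 | 0.674 | 0.783 | 0.851 |
| 7 | 23 | 16 | 0.514 | 0.688 | 0.804 |
| 10 | 20 | 14 | 0.348 | 0.602 | 0.786 |

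Example, k=5, crude: rejection needs 25 − X ≥ 17, so X ≤ 8, and P(Bin(30, 0.25) ≤ 8) = 0.674. Actuarial: apparent control falls from 0.75 to 0.728.

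**Type I error under exclusion** (true control 50%; crude to actuarial): 0.8-2.4%, 0.3-1.4% and 0.1-0.9% for 5, 7 and 10 deaths. It is conservative in general rather than always: with 1 death the actuarial figure is 5.9%, because the z-test cutoff at n=29 is itself liberal (6.8%).

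**If deaths were instead counted as controlled and the 50% benchmark is actuarial.** Apparent control under the null is 1 − F (with exp(−2λp) = 0.5) = 0.553, 0.575 and 0.610 for 5, 7 and 10 deaths. P(Bin(30, 1−F) ≥ 20) = 0.142, 0.204 and 0.331.

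**The case against.** Four points on the other side have weight.

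1. *Power holds when deaths are few.* A reader might infer that power drops below 80% whenever losses stay within the 5 that 30-for-25 allows. The table does not support that: with 1-3 deaths it is 80-91%. The shortfall starts at 4 deaths (13%, inside the 10-15% allowance). On the actuarial reading it is only about 2-4 points at 4-5 deaths.

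2. *Fewer patients may be dropped.* If *progression* in the exclusion means any progression, a patient who dies after distant failure with the field controlled may be kept. The local reading is reasonable, because 6.3 says of patients who progress "They will be followed for local control and survival for 25 months after they have completed their initial radiation", but the text does not settle it. This stands as a limit on the size.

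3. *Inflated type I error is not shown.* A reader might infer that the plan risks a false positive. That requires deaths to be counted as controlled, which is not the reading the text suggests, and the 50% to be actuarial, which is not stated. Nor can the contrast in section 1.0 between 53% local progression-free survival and 39% crude failure in one chemoradiation trial fill the gap. That trial is not a source for the 50%, and local progression-free survival may count deaths as events.

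4. *The 11.2.2 rule is pre-specified and descriptive.* True, and deaths are captured in PFS and OS. But a declared rule can still give a distorted estimate, and this one does.

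**Conclusion.** The point holds as a should-fix. Followed exactly, 11.2.2 overstates the progression proportions relative to cumulative incidence, by 30/(30−k) at 25 months if k of 30 are dropped and nobody else is lost.

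For the primary test, the defect is that the plan does not say how death without in-field progression counts. If the exclusion is carried over, the test becomes generally conservative and loses more power than the smaller sample explains: 67-76% at 4 deaths (82% under random loss), 67-78% at 5 (85%), 51-69% at 7 (80%) and 35-60% at 10 (79%). These figures assume 30 enrolled, 75% true control, no other losses and the local reading of progression. How many such deaths will occur cannot be read from the documents.

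The type I figures of about 14%, 20% and 33% are conditional on two unstated choices and do not bear on the severity.

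**What to change.** 1. **11.2.2.** Replace the exclusion with the cumulative incidence of local, regional, distant and any progression at 13 and 25 months. Treat death without that event as a competing event, and censor loss to follow-up.
2. **5.1.1 and 11.1.1.** State how death without in-field progression counts. Recommended: the Kaplan-Meier estimate of freedom from in-field progression in all treated patients, censoring at death or last scan. State time zero and a rule for patients who die before the first scan after radiotherapy. Declare success if the one-sided 95% log-log lower bound exceeds 50%. State that the 50% benchmark is taken on the same basis, and report cumulative incidence as a sensitivity analysis, noting that it estimates a different quantity.
3. **11.3.1.** State assumed deaths separately from other losses, and restate power for 30 patients under the chosen rule. For Kaplan-Meier, simulation gives about 71-81% as assumed 2-year survival among locally controlled patients goes from 56% to 80%, with type I error about 4%. Allowing for the ±8-week visit window, type I error is 4.6-5.4%. Exclusion over the same range gives 49-75% on the actuarial reading.

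The cost is wording only, with no added patients or visits. Appendix I records scan dates, and 6.4 provides that "Patients will be followed 25 months or until death after the last study radiation treatment for monitoring survival study endpoints". Appendix P has yes/no boxes and one form date, so progression must be dated from the scan record. The downsides are a stated power that may fall short of 80%, and the Kaplan-Meier assumption that death is independent of progression, which the sensitivity analysis must address.
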